Objectives and corresponding endpoints	
Primary objective and corresponding endpoint:
 
To evaluate the short-term and long-term efficacy of the FMD to down-modulate protumor peripheral blood mononuclear cells (PBMCs), including myeloid-derived suppressive cells (MDSCs), and to up-regulate antitumor cells, such as activated T cells and NK cells. Short-term modifications refer to changes assessed the day of FMD discontinuation compared to the day of FMD initiation. Long-term modifications refer to changes detected the day of surgery or 30 days after surgery compared to the day of FMD initiation.
 
Secondary objectives and endpoints:
 
1. To assess by single-cell “mass cytometry” (CyTOF) phenotypic and functional modifications in PBMCs and tumor-infiltrating lymphocytes during the FMD.2. To perform transcriptional and miRNA profiling in PBMCs, tumor cells (Cohort A) and immune cell populations inside lymph nodes (Cohort B).3. To assess changes in the expression of metabolic genes, such as those involved in glycolysis,

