	
trycarboxylic acid cycle, amino acid synthesis, fatty acid and cholesterol de novo biosynthesis in PBMCs.
 
4. To assess FMD-induced changes in blood (glucose, triglycerides, fatty acids, cholesterol, amino acids) and urine (ketone bodies) metabolic parameters.5. To assess FMD-induced changes in plasmatic growth factors, such as insulin, IGF-1, vascular endothelial growth factor (VEGF), platelet-derived growth factor (PDGF), fibroblast growth factor (FGF), IGF1 binding proteins 1 and 3 (IGFBP-1 and IGFBP-3).6. To evaluate by immunohistochemistry (IHC) or multiple immunofluorescence (IF) quantitative and qualitative changes in tumor immune cell infiltrate, including myeloid, T and NK cell markers, by comparing the diagnostic biopsy specimen with the tumor specimen after surgical removal of the primary tumor (Cohort A).7. To assess changes in tumor proliferation index (Ki67), apoptosis (caspase 3 by IHC), autophagy (LC3), glycolysis (Glut1), tumor grade and immunohistochemical expression of estrogen and/progesterone receptor and HER2 oncoprotein in breast cancer patients (Cohort A).8. To evaluate quantitative and qualitative changes in immune cell suspensions from lymph nodes of melanoma patients undergoing one FMD cycle before lymph node dissection (Cohort B).9. To evaluate changes in DNA methylation profiles in tumor and lymph node tissues from patients undergoing the FMD before surgery (Cohorts A and B).10. To assess modifications in gut microbiota community composition, as detected by 16S rRNA gene sequencing and shotgun metagenome sequencing of patient stool samples before and after the FMD.11. To evaluate short-term and long-term modification of systemic nutritional parameters (serum albumin, transferrin, pre-albumin, retinol-binding protein and lymphocyte counts) after one FMD cycle for patients in cohort A and B and after 4 FMD cycles for patients in Cohort C.12. To evaluate changes induced by the experimental treatment in the hematologic profile (white blood cell counts, lymphocyte counts, hemoglobin concentration, platelet counts, red blood cell counts).13. To investigate patient compliance to the diet, as assessed through the analysis of dietary diaries and measured by counting minor and major deviations from the prescribed FMD regimen.14. To assess the tolerability of the prescribed FMD regimen, including adverse events and serious adverse events occurring during the FMD and after its discontinuation.15. To correlate FMD-induced changes in serum metabolites with changes in PBMCs, their activation status, as well as with tumor cell and immune infiltrate characteristics.

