--	--

	
Inclusion criteria
 
Patients eligible for inclusion in this study have to meet all of the following criteria:
 
1. Age \geq 18 and \leq 75 years.
 
2. Evidence of a personally signed and dated informed consent document (ICD) indicating that the patient has been informed of all pertinent aspects of the study before enrollment and FMD prescription.
 
3. Willingness and ability to comply with the FMD protocol, the scheduled visits, treatment plans, laboratory tests and other procedures.
 
4. Histologically confirmed diagnosis of invasive breast cancer candidate to curative surgery (Cohort A), or resected malignant melanoma requiring dissection of the regional lymph node basin for sentinel lymph node involvement (Cohort B), or malignant melanoma treated with curative surgery (including, in case, lymph node removal and lymph node dissection) (Cohort C). For breast cancer patients, any biological subgroup (including estrogen receptor-positive, HER2-positive, triple-negative breast cancer) will be admitted; HER2-positive tumors will be defined on the basis of an IHC score of 3, or a score of 2 with ISH evaluation indicative of gene amplification.
 
5. Availability of archival FFPE tissue blocks of primary breast cancer (Cohort A) or melanoma (Cohort B, Cohort C).
 
6. Presence of an Eastern Cooperative Oncology Group (ECOG) performance status 0 or 1.
 
7. Presence of adequate bone marrow and organ function as defined by the following laboratory values:
 
- ANC $\geq 1.5 \times 10^9/l$- platelets $\geq 100 \times 10^9/l$- hemoglobin $\geq 9.0 \text{ g/dl}$- calcium (corrected for serum albumin) within normal limits or \leq grade 1 according to NCI-CTCAE version 4.03 if not clinically significant- potassium within the normal limits, or corrected with supplements- creatinine $< 1.5 \text{ ULN}$- blood uric acid $< 10 \text{ mg/dl}$- ALT and AST $\leq 2.5 \times \text{ULN}$- total bilirubin $< \text{ULN}$ except for patients with Gilbert syndrome who may only be
--	---

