Study Design and Treatment	
Single-arm, monocentric, prospective study designed to estimate the immunomodulatory and metabolic effects induced by the FMD in breast cancer and melanoma patients.
 
Three different patient cohorts will be enrolled: 1) Cohort A: 40 breast cancer patients candidate to curative surgery without pre-operative systemic treatment. Patients with clinical stages T1N0M0, or those with T1N1M0-T2N0M0 tumors not requiring pre-operative systemic treatment, will be enrolled. Patients with any breast cancer biology, including hormone receptor-positive, HER2-overexpressing and triple-negative cancers, will be included in the study; 2) Cohort B: 40 melanoma patients candidate to lymph node basin dissection after the histological documentation of sentinel lymph node tumor involvement; 3) Cohort C: 20 patients with surgically resected malignant melanoma not candidate to any adjuvant treatment.
 
All patients will be prescribed 5-day low-protein, low-carbohydrate FMD, consisting in a list of allowed foods and quantities to be consumed during each of the five days. Foods or beverages not explicitly included in the prescribed scheme are not permitted. On day 1, the total caloric content of the FMD is of about 700 KCal; on days 2-5, the caloric content is 300 KCal.
 
Patients in Cohort A and B (i.e. those patients receiving the FMD in the pre-operative setting) will receive only one FMD cycle, to be initiated within 15 days from surgery, and to be completed at least 7 days before surgery. Blood, urine and stool samples will be collected just before FMD initiation and at diet completion, to assess FMD-induced effects on systemic immunity and metabolism, as well as the modulatory effects on gut microbiota composition and stool metabolites. Moreover, FMD-induced modifications in the intratumor immune infiltrate and tumor biology (e.g. proliferation index, ER, PgR and Her2 status) will be assessed by comparing diagnostic biopsies with surgical tumor specimens (Cohort A); in Cohort B, the composition of immune cell populations in sentinel lymph node(s) (before the FMD) and in lymph nodes resected at the moment of basin dissection (after the FMD) will be compared as well. Moreover, immune cell suspensions from surgically removed lymph nodes will be obtained from fresh lymph node samples after the FMD to quantify different population subsets, and compared with matched controls of patients with similar characteristics, who were not eligible for enrollment in the trial, or directly refused to be enrolled.

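### Cohort B: sentinel nodes before the FMD versus basin-dissection nodes after it cannot alone identify an FMD effect, and this secondary contrast should be labelled descriptive

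*Protocol*

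**What the plan says.** Study Design and Treatment describes a single-arm study and sets out two nodal comparisons for Cohort B (40 patients).

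- **Within patients.** Immune cell composition "in sentinel lymph node(s) (before the FMD) and in lymph nodes resected at the moment of basin dissection (after the FMD) will be compared".
- **Against controls.** Cell suspensions from fresh nodes, obtained after the diet, are "compared with matched controls of patients with similar characteristics, who were not eligible for enrollment in the trial, or directly refused to be enrolled".

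Inclusion criterion 4 admits patients with "resected malignant melanoma requiring dissection of the regional lymph node basin for sentinel lymph node involvement (Cohort B"). The single pre-operative FMD cycle lasts 5 days and is "to be initiated within 15 days from surgery, and to be completed at least 7 days before surgery".

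Three secondary objectives concern nodes. Objective 8 is about "changes in immune cell suspensions from lymph nodes of melanoma patients undergoing one FMD cycle before lymph node dissection (Cohort B"). Objective 2 includes profiling of "immune cell populations inside lymph nodes (Cohort B"). Objective 9 covers "changes in DNA methylation profiles in tumor and lymph node tissues from patients undergoing the FMD before surgery (Cohorts A and B").

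Statistical methodology includes lymph node immune patterns significantly altered by the diet in the project's main goal. It bases analysis on descriptive statistics, prefers non-parametric tests (signed-rank for paired data), mentions Hommel's adjustment and sets a two-sided 5% threshold. It says nothing specific about how the sentinel-versus-dissection contrast is to be interpreted.

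**The concern.** A before/after comparison supports a treatment effect only if little else changes between the two measurements. Here the two specimens are different nodes, removed at different operations, and the first is selected because disease was found on the sentinel side. A difference in immune composition could come from the kind of node, the earlier sentinel surgery, the time between operations, tumour involvement or the diet.

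Because the main goal names lymph node patterns and nothing restricts this contrast, a significant difference could be reported as immunomodulation by the FMD. The stake is a wrong nodal conclusion that might be carried into later combination studies. The primary objective concerns peripheral blood cells and does not use these specimens.

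**Working it through.** **1. What changes together with the diet.**

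| Feature | Before FMD | After FMD | Separable within the pairs? |
|---|---|---|---|
| Node type | sentinel | basin dissection | No, same in every patient |
| Sentinel surgery already done | no | yes | No, same in every patient |
| Time | earlier | later | Could be modelled if it varies, but never zero |
| Tumour involvement | required on the sentinel side | no condition stated | Possibly, by stratifying on histology |

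**2. Minimum gap.** If day 5 of the FMD is at least 7 days before surgery, day 1 is at least 7 + 4 = 11 days before. The sentinel node precedes day 1, so the gap is longer still. The 15-day limit applies to starting the FMD, not to the sentinel procedure, so the gap has no stated upper limit.

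**3. Identification.** Let D be the dissection value minus the sentinel value in one patient. Then

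E(D) = FMD effect + node type + prior surgery + time + any involvement imbalance.

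The first three terms are present in every pair. More pairs estimate the sum more precisely but do not split it. Hommel's procedure controls chance rejections of E(D) = 0. It does not turn that null hypothesis into one of no FMD effect.

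**4. Illustrative size.** The plan gives no effect size, SD or power for Cohort B, so there is no power figure to reproduce (the cohort sizes do add up: 40 + 40 + 20 = 100). The non-diet shift and the number of evaluable pairs are assumptions.

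Smallest observed mean difference reaching two-sided p < 0.05 by a paired t test, t(0.975, n−1)/√n, in SDs of the paired differences:

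- n = 40: 0.320
- n = 30: 0.373
- n = 20: 0.468

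Simulated signed-rank rejection rates with normal differences and no FMD effect (40,000 runs per cell; Hommel 3,000 runs, 10 independent indicators, one of them shifted):

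| Assumed non-diet shift (SD) | 0 | 0.2 | 0.3 | 0.5 | 0.8 |
|---|---|---|---|---|---|
| 40 pairs, unadjusted | 5% | 23% | 44% | 85% | >99% |
| 20 pairs, unadjusted | 5% | 13% | 24% | 55% | 91% |
| 40 pairs, Hommel | – | 5% | 14% | 53% | 97% |
| 20 pairs, Hommel | – | 1% | 4% | 17% | 56% |

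A separate 10,000-run simulation at 40 pairs agrees within simulation error, and the exact paired t power is within 0.02.

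**5. What a control group would do.** Subtracting the same sentinel-to-dissection difference in patients without the FMD cancels the non-diet terms if they are equal in both groups. In 3,000 runs per setting (Mann-Whitney, 40 patients against 20 or 40 controls) the rejection rate was then 4.5% to 5.4% for every shift from 0 to 1.0 SD. The planned controls are described only for fresh post-FMD suspensions, and no control sentinel specimens are mentioned.

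**The case against.** The strongest reply is that the study is openly single-arm, bases its analysis on descriptive statistics and concedes that its statistical properties cannot be estimated in advance. It also already adds matched controls for the suspensions named in objective 8, and interpretive limits often sit in an SAP. This lowers the weight of the point. It does not remove it, because the difficulty lies in the specimens chosen and no later model of these pairs resolves it.

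Several stronger readings are tempting, but the documents do not support them.

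- *Tumour involvement differs in every pair.* Involvement is required on the sentinel side, but nothing says dissection nodes are free of disease, and not every sentinel node need be involved. It may be unbalanced and could be stratified on.
- *The plan commits to a 5% test of this contrast.* It sets a threshold for two-sided tests and assigns no test here. The diet-induced wording that precedes the contrast belongs to the Cohort A clause.
- *Sentinel tissue is not assured by eligibility.* Criterion 5 asks for "Availability of archival FFPE tissue blocks of primary breast cancer (Cohort A) or melanoma (Cohort B, Cohort C"), and it is unclear whether the word primary governs melanoma. The number of evaluable pairs is therefore only an assumption above.
- *Objectives 2 and 9 use the same flawed contrast.* Neither names a nodal comparator. The limit applies only if a sentinel-versus-dissection contrast is used for them.

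It is also fair to say that the rejection rates are ordinary power values under assumed shifts and reveal nothing about actual nodes.

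**Conclusion.** The point holds as a limit on one secondary contrast. Node type and prior sentinel surgery are fully aliased with FMD exposure, elapsed time is never zero, and involvement may be unbalanced. The pairs alone therefore cannot identify an FMD effect at any sample size. That conclusion follows from the text and needs no outside figure.

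The illustrative rates rest on assumed shifts, assumed numbers of pairs, normal differences and, for Hommel, ten independent indicators with one shifted. A rejection becomes a false FMD finding only if it is attributed to the FMD. A reader might infer that the trial's main result is compromised, but the primary PBMC objective does not depend on these nodes. The change is worth making because it is nearly free and alters what may be concluded from the nodal pairs.

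**What to change.** In Study Design and Treatment, Cohort B:

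1. Add wording such as: *The sentinel-versus-dissection comparison is descriptive. A difference within these pairs alone will not be attributed to the FMD, because node type, prior sentinel surgery, elapsed time and possibly tumour involvement differ. The same limit applies to any sentinel-versus-dissection contrast used for objectives 2 or 9.*
2. Base nodal inference about the FMD on the planned comparison of post-FMD suspensions with matched controls. State that dissection nodes are used in both groups, and report it as non-randomised with residual selection bias.
3. As an exception to item 1, if sentinel tissue from those controls already exists, a difference-in-differences against them may be reported with the same caveat.

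**Cost.** Item 1 is wording only. Item 2 is wording only if control nodes are dissection nodes, as the text suggests; it supplies no control for objectives 2 and 9. Item 3 depends on tissue the protocol does not document.

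**Downside.** Fewer nodal findings can be called FMD effects, and the between-group comparison is less precise. With 80% power at two-sided 5% (two-group t test), the detectable difference is about 0.63 between-patient SD for 40 versus 40, 0.78 for 40 versus 20 and 0.91 for 20 versus 20. These group sizes are assumed, since no control number is given. The comparison also has its own bias. Ineligible controls could include patients excluded for systemically treated autoimmune disease, HIV or corticosteroid use (exclusion criteria 10, 14 and 21), all plausibly relevant to immune cells, and refusers may differ in other ways.

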
	Patients in Cohort C will receive four consecutive FMD cycles every 28 days. Blood, urine and stool samples will be collected before and after FMD cycles n.1 and n.4, as well as 30 days after completion of 4 FMD cycles, to assess short- and long-term changes in systemic metabolism and immunity.
Duration of the treatment	Enrolled patients will undergo the experimental intervention (namely the FMD) for one cycle (Cohorts A, B) or 4 consecutive cycles (Cohort C). The intervention will be interrupted in the case of unacceptable toxicities, consent withdrawal, patient death or for other reasons at the discretion of the Investigators.
Planned sample size	100 patients (40 in cohort A; 40 in cohort B; 20 in cohort C)
Study period	30 months of enrollment and 6 months of follow up

Statistical methodology	
The main goal of this project is to find systemic, tumor or lymph node immunologic modulation patterns that are significantly modified by the FMD. This assessment will be made on the basis of many indicators belonging to distinct biological systems, while a synthetic criterion for judging treatment effectiveness on this ground is lacking. This situation precludes the possibility to estimate upfront the statistical properties of our study. Nevertheless, the planned sample size in the three patient Cohorts was chosen in the attempt to guarantee study feasibility and patient enrollment within two years from study initiation, while contemporarily providing a sufficient patient number to describe the eventual variability in FMD-induced immunological, metabolic and gut microbiota modifications. The analysis of study results will be based on calculation of descriptive statistics suitable for continuous (mean, median, standard deviation, interquartile range) or categorical (absolute/ relative frequencies) variables. Statistical testing will be preferably based on non-parametric location tests for bivariate comparisons like the Wilcoxon-Mann-Whitney test or the Wilcoxon Signed-Rank Test in case of paired data. Generalized linear models will also be used for a comprehensive analysis of longitudinal data. Finally, robustness of statistical results focusing on single variables will be checked using suitable adjustments for multiple testing, like the Hommel's procedure (1988) for controlling the family wise error rate (FWER). The conventional 5% threshold of statistical significance for two-sided tests will be used throughout.

--------------------------------	--

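### Does naming generalized linear models for longitudinal data, with no mention of the patient, make the repeated-measures analysis invalid?

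*Protocol*

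**What the plan says.** The Statistical methodology section gives a short analysis plan. Descriptive statistics come first. Testing is then to be preferably non-parametric, using "the Wilcoxon-Mann-Whitney test or the Wilcoxon Signed-Rank Test in case of paired data". The next sentence adds: "Generalized linear models will also be used for a comprehensive analysis of longitudinal data". Hommel's procedure is named as a check on robustness, and "The conventional 5% threshold of statistical significance for two-sided tests will be used throughout".

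The sampling schedule is in Study Design and Treatment. For Cohorts A and B (40 patients each), "Blood, urine and stool samples will be collected just before FMD initiation and at diet completion". For Cohort C (20 patients), "Blood, urine and stool samples will be collected before and after FMD cycles n.1 and n.4", with one more collection 30 days after the fourth cycle. The primary objective adds a later time point: "Long-term modifications refer to changes detected the day of surgery or 30 days after surgery compared to the day of FMD initiation".

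The protocol mentions no random patient effect, generalized estimating equations (GEE), clustered variance or correlation structure. It also does not say that a patient term will be left out.

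**The concern.** A generalized linear model in the strict sense takes observations as independent given the covariates. Repeated samples from one patient are not independent. If the samples were entered as separate rows with no patient term, the standard errors would be wrong. For a change over time in measured levels they would be too large, because the model ignores that each patient serves as his or her own control. For a comparison between groups of patients they would be too small, because several samples from one patient would count as several patients.

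This is the only sentence in the protocol that covers all occasions in one model, and Cohort C has the fewest patients and the most samples. A supplementary model that missed changes visible in the paired tests would confuse the interpretation. Hommel's adjustment cannot repair p-values that are wrong to begin with.

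**Working it through.** The protocol gives no power, effect size, standard deviation or correlation, so there is no stated figure to reproduce.

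**Samples per patient**

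- Cohorts A and B: 2 (start and end of the diet), or 3 with the later time point in the primary objective.
- Cohort C: 2 + 2 + 1 = 5.

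**Assumptions.** Normal data, equal variance σ² at each occasion, and the same correlation ρ between any two samples of a patient, with ρ taken as 0.3, 0.5 and 0.7. The test is two-sided at 5%, as in the protocol.

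**Change over time, levels as outcome, no patient term.** For two occasions in n patients:

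- true variance of the difference in means: 2σ²(1 − ρ)/n
- variance under independence: 2σ²/n
- ratio of standard errors: 1/√(1 − ρ)
- actual type I error: 2[1 − Φ(1.96/√(1 − ρ))]
- power kept by a test that would have 80% if analysed correctly: Φ(2.80 − 1.96/√(1 − ρ)), where 2.80 = 1.96 + 0.84

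| ρ | SE ratio | Type I error | Power instead of 80% |
|---|---|---|---|
| 0.3 | 1.20 | 1.9% | 68% |
| 0.5 | 1.41 | 0.56% | 51% |
| 0.7 | 1.83 | 0.035% | 22% |

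Simulation agrees in direction and size. With 20 patients, 5 samples each and ρ = 0.5, the naive standard error was 1.38 times the true one and the rejection rate under no effect was 0.9%.

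**Overall time test in Cohort C.** With an assumed shift of 0.6 SD at all later occasions (20,000 simulated trials per cell), power at ρ = 0.3/0.5/0.7 was 35%/29%/21% without a patient effect and 59%/76%/94% with one.

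**The test the protocol prefers.** The signed-rank test on two occasions uses one difference per patient, so there is no clustering to mishandle. For the same 20 patients and 0.6 SD shift, its simulated power was 54%/69%/89%. For 40 patients and a 0.4 SD shift it was 53%/66%/87%.

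**Which analyses are exposed.** The primary objective defines the short-term change and the long-term change separately, each against the day of FMD initiation. Each is a comparison of two occasions, so the signed-rank test covers it. With only two samples, a model of the change also has one row per patient and is unaffected. What remains is the supplementary model with three or more occasions, mainly in Cohort C.

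**The case for a change.** The strongest case for a change is that the protocol is not silent here: it names a model class and assigns it to repeated measurements, and that class does not handle the correlation by default. The error can also run in the dangerous direction. If changes from FMD initiation were stacked over occasions and averaged with no patient term, changes sharing a baseline would correlate 0.5 whatever the value of ρ. The design effect would be 1 + (m − 1) × 0.5, which is 2.5 for four changes and 1.5 for two. The true type I error would then be 2[1 − Φ(1.96/√2.5)] = 21.5%, or 2[1 − Φ(1.96/√1.5)] = 11.0%.

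The arithmetic is right, but the protocol states no such analysis. It defines short-term and long-term change separately and nowhere averages them. The same holds for comparing levels between Cohorts A and B pooled over occasions: the study is single-arm, the cohorts have different diseases, and no such comparison is described. Nor does the protocol propose a model for binary indicators with patient as a fixed factor. Its reference to "categorical (absolute/ relative frequencies) variables" concerns descriptive statistics.

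What stands is that the wording is loose. The term is, however, often used broadly enough to include GEE and mixed models. Authors who ask for a paired test on paired data in the preceding sentence have plainly recognised dependence within a patient.

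**Conclusion.** No change to the plan is needed. The problem arises only if an analyst fits an independence model to data that the protocol itself calls longitudinal, and nothing in the protocol asks for that. Whether to use a patient random effect or to cluster on patient, and which small-sample correction suits 20 patients, belongs in an analysis plan. The choice also deserves more thought than a change of label, because for binary outcomes mixed models and GEE estimate different quantities.

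If the literal reading were followed, the time contrasts on levels would be too cautious: standard errors 1.20 to 1.83 times too large for correlations of 0.3 to 0.7. This would occur in supplementary models, mainly in Cohort C, while the preferred paired tests stay valid. These figures rest on assumed correlations, normality and equal correlation between occasions, none of which the protocol gives. Naming the patient term would be a harmless clarification, but the conclusions on the primary objective do not depend on it.

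### Should the protocol say whether the nominal or the Hommel-adjusted p-value decides that an immune change is significant?

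*Protocol*

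**What the plan says.** The Statistical methodology section of the protocol gives the main goal as finding "immunologic modulation patterns that are significantly modified by the FMD". It says that many indicators will be used, that no single synthetic criterion of effectiveness exists, and that the study's statistical properties therefore cannot be estimated in advance. Analysis rests on descriptive statistics, Wilcoxon-type tests and generalized linear models.

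On multiplicity it says that "robustness of statistical results focusing on single variables will be checked using suitable adjustments for multiple testing", gives Hommel's procedure as an example, and states its purpose as control of the family-wise error rate. The closing sentence is "The conventional 5% threshold of statistical significance for two-sided tests will be used throughout".

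The primary objective (Objectives and corresponding endpoints) concerns protumor blood cells, "including myeloid-derived suppressive cells (MDSCs), and to up-regulate antitumor cells, such as activated T cells and NK cells". It has a short-term and a long-term window and no order of priority. Study Design and Treatment describes a single-arm study meant to estimate effects.

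**The concern.** A robustness check usually follows a result that has already been declared. On that reading nominal p-values decide, the adjustment comes afterwards, and nothing is said about a result that fails it. On the other reading the 5% threshold also covers the adjusted p-values, and these decide. The text does not choose.

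The point touches the primary objective, which has at least three named cell populations and two windows. With no synthetic criterion, single-variable significance is the likely way to reach the stated goal, so it matters which p-value counts. If a marker were reported as significantly changed although it failed the protocol's own check, it could become a false lead for the combination studies that the Hypothesis/Rationale section says this work should inform.

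**Working it through.** The protocol gives no power, effect size or number of tests, so it has no figure to reproduce. The stated 5% level is an input and holds for one test.

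**Inputs from the protocol.** Two-sided 5%; three named populations; two windows; cohorts of 40, 40 and 20.

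**Assumptions.** The cell types are given as examples, so the number of tests is assumed. So are the correlations between test statistics.
- 6 tests: 3 populations × 2 windows, cohorts pooled.
- 12 tests: by cohort, following the blood sampling described. For Cohorts A and B this is "Blood, urine and stool samples will be collected just before FMD initiation and at diet completion" (3 short-term tests each). For Cohort C it is "before and after FMD cycles n.1 and n.4, as well as 30 days after completion of 4 FMD cycles" (3 short-term and 3 long-term tests). So 3 + 3 + 6 = 12.
- 18 tests: 3 × 2 × 3. This needs long-term blood in Cohorts A and B, which the sampling description does not list.

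**Chance of at least one nominal p ≤ 0.05 when nothing changes.** For k independent tests it is 1 − 0.95^k:
- k = 6: 1 − 0.95^6 = 0.265
- k = 12: 1 − 0.95^12 = 0.460
- k = 18: 1 − 0.95^18 = 0.603

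For correlated tests it was simulated (300,000 runs, normal statistics, equal correlation within a cohort, cohorts independent because they are different patients). Under this global null the Hommel procedure rejects something exactly when the Simes test does.

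| Tests | Rule | ρ = 0 | 0.3 | 0.5 | 0.8 |
|---|---|---|---|---|---|
| 6 | nominal | 26% | 24% | 21% | 14% |
| 12 | nominal | 46% | 43% | 39% | 30% |
| 18 | nominal | 60% | 56% | 50% | 36% |
| 6 | Hommel decides | 5.0% | 4.8% | 4.4% | 3.5% |
| 12 | Hommel decides | 5.0% | 4.9% | 4.7% | 3.9% |

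**Price of making the adjusted p-value decisive.** The smallest paired change detectable with 80% power, in SDs of the change, comes from the one-sample noncentral t, divided by √(3/π) for the signed-rank test. The Bonferroni level 0.05/12 = 0.0042 is a bound, since Hommel is never less powerful.
- n = 40: 0.47 SD at 5%, 0.63 SD at 0.05/12.
- n = 20: 0.68 SD at 5%, 0.95 SD at 0.05/12.

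Put the other way, a change with 80% power at 5% has about 44% (n = 40) or 41% (n = 20) at 0.05/12.

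**The case for a change.** The case for a change is that the protocol is not silent. It gives the adjustment a role, robustness, beside a fixed 5% threshold, and a later plan that made adjusted p-values decisive would have to reinterpret that wording. One sentence using the sponsor's own procedure would settle it, and even the lowest nominal figure, 14%, is almost three times 5%.

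Part of this stands. The wording is loose, the arithmetic is right, and stating the rule would do no harm to a sponsor who always meant adjusted p-values to decide. It does not amount to a defect, for these reasons:
- Multiplicity, a procedure and its error target are all named, and the threshold sentence comes directly after them. Reading 5% as also applying to the adjusted p-values is natural, and on that reading, if they decide, the error is held.
- The suggested rule cannot operate without a list of tests, a family and a choice between pooled and by-cohort testing. These commonly sit in a statistical analysis plan, which is not at hand. An analyst can fix the rule there without contradicting the protocol.
- No success criterion or go/no-go decision hangs on one p-value. Reporting nominal results beside an adjusted check is a defensible convention in exploratory work, and a reader given both can see which markers fail.
- The goal is stated as patterns across many indicators, whereas the Hommel check covers single variables. A claim rule for each marker goes beyond what the protocol sets out to do.

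**Conclusion.** No change to the plan is called for. This is a gap that analysts fill sensibly, joined to a fair trade-off: strict family-wise control would lower the chance of a false lead from 14–46% (6 or 12 tests) to about 5% or less, but could cut power for a real change from 80% to as low as 41–44% at the 12-test bound. For a lead-finding study with cohorts of 20 to 40, reasonable statisticians would differ on that exchange.

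All the error rates rest on assumed test counts, assumed correlations and the global null; none comes from the protocol. Reporting nominal and adjusted p-values side by side, and describing results that pass only the nominal threshold as exploratory, would follow the protocol as written.

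The test counts also depend on a separate matter. The primary objective says "Long-term modifications refer to changes detected the day of surgery or 30 days after surgery compared to the day of FMD initiation", while the blood sampling described in Study Design and Treatment lists neither time for Cohorts A and B and uses 30 days after the fourth cycle for Cohort C. Those passages need to be reconciled, but that is a different point and adds no weight to this one.
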